- Current substance disorder other than marijuana, nicotine and caffeine as assessed by self-report and urine toxicology screen at baseline;
- Current use of medications that may interact with study medications;
- History of hypersensitivity to study medications;
- Clinically significant electrolyte abnormalities, current rhinitis or use of vasoconstricting medications or prostaglandins.

NOTE: the exclusion criteria are based in reducing participants' safety.

Participants need to speak English and be able to understand informed consent and questionnaires in English which will be written exclusively at an 8th grade level.

One hundred individuals receiving buprenorphine/naloxone or methadone as opioid replacement therapy (ORT) will be screened, 80 will be randomized, with 50 expected to complete the study. Potentially eligible participants will be invited for an in-person screening, where they will provide written informed consent and undergo a physical examination in the NEW Clinical Laboratory Core (CLC).

The **sample size estimate** is based on recent findings reporting that baseline levels of stress significantly predicted oxytocin effects on cue-induced craving (Mitchell et al., *J Addict Med*, 2016). Effect sizes were calculated based on a between-subjects in oxytocin study with alcohol related responses (Pedersn et al., *ACER*, 2013). The estimate of opioid craving (measured by the OCQ) were calculated from the *M* and the *SD* of alcohol-related outcomes: oxytocin was superior to placebo in reducing alcohol withdrawal (*i.e.* less lorazepam required to complete detoxification: 3.4 mg±4.7, vs. 16.5 mg±4.4, p<0.01), lower mean CIWA scores (4.3 mg±2.3 vs. 11.8 mg±0.4, p<0.01). We estimated that with a standard threshold, α = 0.05, for med-large effect (f = 0.35), two group independent variable and three covariates in ANCOVA, the *N* is 67 to detect 0.80 power. With an additional 0.20 to account for attrition [N = 50 (completers) + 13 = 80 (enrolled)]. The estimated power at N = 67, with the addition of an interaction term (for Aim 2) would be = 0.63. Therefore, the calculated sample size is well powered to address the hypothesis of the main medication effect (Aim 1) and of the interaction effect with stress and anxiety (Aim 2).

5. Recruitment Methods

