- 1. Amount of missing data in the dataset:
 - a. Oxytocin condition: 10% did not receive either oxytocin or placebo condition (within subject, *n*=16; between subject, *n*=4)
 - b. Yohimbine condition: 11.12% did not receive yohimbine condition (yohimbine, *n*=14; placebo, *n*=16; no yohimbine, *n*=4):

- 2. Reason for missing:
 - a. Oxytocin condition: change from between subject to within subject design
 - b. Yohimbine condition: safety concerns due to past history of cardiovascular disease and/or current hypertension (*n*=3), stroke (*n*=1)

3. Consequences:

- a. *Oxytocin condition*: no differences between participants with and without missing values except there were no subject taking methadone in the subjects with missing values.
- b. *Yohimbine condition*: no differences between participants with and without missing values except there were cardiovascular concerns in the subjects with missing values.
- 4. *Method*: GLM with MNAR using all available pairs of data to model missing values with maximum likelihood estimation
- 5. Software: IBM SPSS Statistics for Windows, version 29 (IBM Corp., Armonk, NY, USA)

All statistical analyses were performed after participants had completed their follow-up visits and the study database had been locked. The results were presented using summary statistics: number of subjects (n); mean (M); standard deviation (SD) or frequency distributions (%) and effect size was reported as Cohen's d.

All statistical procedures were performed by IBM SPSS Statistics for Windows, version 29 (IBM Corp., Armonk, NY, USA), and GraphPad Prism (v.10) was used to generate figures (La Jolla, CA, USA). All statistical tests were two-tailed, and statistical significance was accepted if an alpha value p<.05 was obtained.

References

1. FDA. Changes or modifications during the conduct of a clinical investigation; final guidance for industry and CDRH staff. 20012001.

Schulz K, Altman D, Moher D. Consolidated Standards of Reporting Trials Group CONSORT
2010 Statement: Updated Guidelines for Reporting Parallel Group Randomised Trials. Bmj.
2010;340:c332.

4. Tukey JW. The future of data analysis. The annals of mathematical statistics. 1962;33(1):1-67.

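### The planning effect f = 0.35 does not follow from the alcohol-withdrawal means and SDs that the protocol offers as its source, and the documents give no other derivation

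*Protocol*

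**What the plan says.** All of the material is in one paragraph, the sample size estimate in Protocol Part III, section 4 (Participant Population).

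- It opens by citing a study in which baseline stress predicted oxytocin's effect on cue-induced craving. No mean, SD or effect size is given from that study.
- It then names a different source for the effect size: "Effect sizes were calculated based on a between-subjects in oxytocin study with alcohol related responses".
- It carries that source over to craving: "The estimate of opioid craving (measured by the OCQ) were calculated from the *M* and the *SD* of alcohol-related outcomes".
- It prints two outcomes, introduced by the statement that "oxytocin was superior to placebo in reducing alcohol withdrawal". The first is "less lorazepam required to complete detoxification: 3.4 mg±4.7, vs. 16.5 mg±4.4, p<0.01". The second is the mean CIWA score, 4.3 ± 2.3 against 11.8 ± 0.4.
- A new sentence sets the planning value, "for med-large effect (f = 0.35), two group independent variable and three covariates in ANCOVA", and concludes that "the *N* is 67 to detect 0.80 power".
- It gives power of 0.63 at N = 67 once an interaction term is added, and ends by calling the sample size well powered for Aims 1 and 2.

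The SAP (Statistical analysis) gives no effect size. It says only that the target sample size weighed power against feasibility in a preliminary trial.

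**The concern.** A reader takes the paragraph as a chain: published oxytocin data, then an effect size, then N. The link from the data to 0.35 is not shown, and the printed numbers do not produce it. The outcomes are also of a different kind. One is the amount of medication needed to complete alcohol detoxification and the other is an alcohol withdrawal score, whereas Aims 1 and 2 concern opioid craving after cues.

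At stake is how far the claim of adequate power can be trusted. The effect size is the input to which N is most sensitive. If it is in fact a judgement, a reader interpreting a null craving result needs to know that, and should not believe that prior oxytocin data support a medium-to-large effect.

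**Working it through.** **Inputs.** From the protocol paragraph: two groups, three covariates, ANCOVA, f = 0.35, power 0.80, and "with a standard threshold, α = 0.05". The F test is non-directional, which agrees with the SAP: "All statistical tests were two-tailed, and statistical significance was accepted if an alpha value p<.05 was obtained". Also the two pairs of means and SDs above. The source study's group sizes are not given, so equal groups are assumed first and then varied.

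**1. Reproduce the plan's figure.** Power is P(F′ > F crit), where F′ is noncentral F with numerator df = 1, denominator df = N − 2 − 3 = N − 5, and noncentrality λ = f²N.

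- At f = 0.35 and N = 67: λ = 0.1225 × 67 = 8.21, df = 1 and 62, power = 0.805. At N = 66 power is 0.799.
- So N = 67 is right given f = 0.35. The stated 0.63 is also recovered if the test has 3 numerator df (0.635).

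**2. Effect sizes from the printed figures.** d = |M1 − M2| / √[(SD1² + SD2²)/2], and f = d/2 for two equal groups.

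| Outcome | Difference | Pooled SD | d | f | f ÷ 0.35 |
|---|---|---|---|---|---|
| Lorazepam | 16.5 − 3.4 = 13.1 | √[(22.09 + 19.36)/2] = 4.55 | 2.88 | 1.44 | 4.1 |
| CIWA | 11.8 − 4.3 = 7.5 | √[(5.29 + 0.16)/2] = 1.65 | 4.54 | 2.27 | 6.5 |
| Planned | – | – | 0.70 | 0.35 | 1 |

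In the same ANCOVA these two effects would need a total N of about 9 and 7 for 0.80 power, against 67.

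**3. Could another reading give 0.35?**

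- *Unequal source groups.* With one group holding 20% to 80% of the sample, f runs from 1.13 to 1.44 (lorazepam) and from 1.45 to 2.75 (CIWA).
- *Larger SD only.* f = 1.39 and 1.63.
- *± values as standard errors, against the SD label.* Then f = d/(2√n), and f = 0.35 needs n = (d/0.70)² per group: about 17 for lorazepam and about 42 for CIWA. Either outcome alone could give 0.35 at a suitable group size, but no single group size does so for both. The source's group sizes are not in the documents, so this reading can be neither confirmed nor excluded.

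No variant tried that treats the values as SDs gives f below 1.13.

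**4. How much the choice of f matters**, in the protocol's between-subjects ANCOVA:

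| f | Power at N = 67 | N for 0.80 power |
|---|---|---|
| 0.35 | 0.81 | 67 |
| 0.30 | 0.68 | 90 |
| 0.25 | 0.52 | 128 |
| 0.20 | 0.36 | 199 |

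**The case against.** Five points can fairly be made for the protocol.

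- *The text never equates 0.35 with the printed values.* It says effect sizes were calculated from the alcohol study, then begins a new sentence with a value labelled medium-to-large, which could be a conventional or discounted planning figure. This stands as a limit on the wording: the documents do not show how 0.35 was chosen. It does not remove the problem, because the paragraph says a calculation was made and offers no other numerical source.
- *A craving study is cited.* True, but without a number, so it cannot support 0.35 as written.
- *The ± values may be standard errors.* As shown, that could yield 0.35 for one outcome at an unseen group size. It contradicts the protocol's own label and would still leave a withdrawal measure standing in for craving.
- *0.35 is far below what the printed data imply, so N is if anything cautious.* The mismatch indeed does not show that N is too small. A reader might infer under-sizing from this point; the documents do not support that. Nor do they support calling 0.35 cautious, since withdrawal outcomes do not establish what is cautious for craving.
- *The SAP no longer leans on this derivation and the trial moved to a within-subject design.* This limits the practical effect: correcting the paragraph alters no enrolment or analysis. The protocol paragraph is nevertheless still its stated basis for sample size and its claim of adequate power.

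A reader might also conclude that 0.35 was definitely not derived from the alcohol study. The documents cannot settle that. They show only that the printed figures, read as labelled, do not produce it.

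**Conclusion.** The point holds as a fault in the stated justification. The protocol presents its craving effect as calculated from alcohol-study means and SDs. The printed figures give f = 1.44 and 2.27, measure withdrawal, and do not lead to the 0.35 on which N = 67 rests. Neither document gives a numerical craving effect. The arithmetic from 0.35 to 67 is correct.

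The values 1.44 and 2.27 assume equal source groups and the SD label; varying the allocation, or using the larger SD, leaves every value at 1.13 or above.

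The claim of adequate power is therefore conditional on an unsupported input. It is also strained at f = 0.35 itself: the same ANCOVA gives about 0.68 for the 50 expected completers, and the protocol's own figure with the interaction term is 0.63. All these powers belong to the two-group between-subjects design with which the trial began. They do not describe the power of the current crossover, which could be higher or lower depending on the within-person correlation and the number of completers.

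**What to change.** In the sample size paragraph of Protocol Part III, section 4:

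1. Replace the statement that the effect was calculated from alcohol-related means and SDs with the actual step from a craving effect to f = 0.35, naming the source and the craving instrument. If there is no such step, label f = 0.35 as an assumed craving effect and remove the lorazepam and CIWA figures as its basis.
2. State adequate power only as conditional on that assumption, with power at the planned number over a range of f. For the present between-subjects ANCOVA at N = 67, the values are those in the table above for f = 0.20 to 0.35. Report the power for 50 completers and for the interaction beside them, so that the conditional wording does not conceal those shortfalls.
3. Redo the calculation for the within-subject oxytocin-by-yohimbine crossover, with the within-person correlation stated as an assumption and varied. A between-subjects table alone would not describe the trial as now designed.

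Cost: items 1 and 2 are wording, and item 3 is one short calculation. No additional participants and no change to conduct or analysis. The stated basis for the sample size will read less favourably.

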In this double-blind, placebo controlled, randomized trial, individuals with OUD (*N*=50) who are currently receiving treatment with buprenorphine/naloxone or methadone will be randomized to intranasal oxytocin (40 international units, IU) and oxytocin-matched placebo, administered twice/day for 7 days with a minimum of two days between the opposite condition (oxytocin or placebo). On days 5 and 7, and on days 14 and 16, participants will complete two counter-balanced sessions in which they receive yohimbine (32.4 mg) or yohimbine-matched placebo, and responses to opioid cues are assessed.

Aim 1: assess the effects of oxytocin on cue-induced opioid craving after yohimbine stress-induced. We hypothesize that opioid craving will be reduced in the oxytocin condition, compared to the oxytocin-matched placebo, after yohimbine stress induction.

Aim 2: assess whether baseline levels of stress affect the effects of oxytocin on cue-induced opioid craving after yohimbine-matched placebo. We hypothesize that after yohimbine-matched placebo administration, opioid craving will be reduced in the oxytocin condition only among individuals with higher levels of stress at baseline.

Aim 3: to assess the safety and tolerability of oxytocin and yohimbine in OUD individuals receiving buprenorphine/naloxone or methadone. Participants will complete a laboratory session that includes a battery of medical/physiological/psychological assessments to monitor adverse events.

Aim 4:

Exploratory Aims: we will examine the effect of oxytocin, as compared to placebo, on neuroendocrine fluctuations of salivary cortisol (three points area under the curve) and blood neurotensin, orexin and substance P by comparing hormones concentrations at baseline and after study medication and placebo administration (visit 3, 4, 5 and 6).

This research will be the first to assess the clinical efficacy of repeated oxytocin administration to prevent opioid stress-induced relapse. Considering the high comorbidity between OUD, anxiety disorder and PTSD, this proposal will pave the avenue for testing oxytocin as an adjunct opioid replacement therapy (ORT) for an as needed personalized pharmacotherapy for this population.

[figure not shown]

If your study ONLY involves the use of identifiable secondary data / biospecimens, including coded data from which you may be able to ascertain identity, skip to PART VI. Otherwise, please continue.

3. Materials, Methods and Analysis.

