This study will use a within subject design with oxytocin vs. oxytocin-matching placebo and yohimbine vs. yohimbine-matching placebo. The cue reactivity (CR) (opioid craving induced by personalized opioid cues) will follow the physiological symptoms (triggered by yohimbine) to isolate the stress signal associated with opioid. Eligible participants will be randomized to use intranasal oxytocin or placebo spray under double-blind conditions for 7 days. On days 5 and 7, participants will complete a session in which they receive yohimbine and one in which they receive placebo, under double-blind conditions, with the order of these conditions randomized across participants. After a two-day wash-out period, participants will receive the opposite condition within the oxytocin group (oxytocin or placebo, counterbalanced) to be administered for 7 days. On days 14 and 16, participants will complete an additional two labs where they will receive yohimbine and yohimbine matched placebo (counterbalanced). In a follow-up visit, we will complete final assessments before concluding the study (**Figure 1**).

FIGURE 1 - Pharmacological interventions during the study

Drugs and Doses Participants will receive intranasal oxytocin (40 IU) and oxytocin-matched placebo twice a day for 14 days; there will be one week of oxytocin administration and one week of placebo administration with two days of washout between the two conditions. They will receive two oral doses of yohimbine (32.4 mg) and two oral doses of yohimbine-matched placebo in the laboratory sessions.

[name] already obtained the Investigational New Drug (IND: 135570) from FDA for this study (Appendix A).

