Assessments: The CADRE CLC will provide a core assessment battery to all RPs to measure mechanisms underlying chronic disease. As described in the CLC Research Plan, these include measures of pain, trauma, family history of AUD/SUD, affect, behavioral dysregulation, physical activity, health-related quality of life. Biomarkers collected in all projects include: sleep, enzymes aminotransferase and alanine aminotransferase (AST, ALT), markers damage; creatinine and blood urea nitrogen, markers of kidney function; salivary cortisol, a marker of stress response; soluble CD14 (sCD14), a marker of monocyte activation; tumor necrosis factor alpha (TNF-α) and interleukin-6 (IL-6), pro-inflammatory cytokines; kynurenine/tryptophan ratio (Kyn/Tryp), implicated in neuropsychiatric symptoms associated with immune activation; and monocyte chemoattractant protein 1 (MCP-1), a chemokine that regulates migration and infiltration of monocytes/macrophages and is involved in various neuroinflammatory disorders.

THE BLUE TEXT IN THE FOLLOWING SECTIONS IS A GUIDE TO ENSURE ALL RELEVANT INFORMATION IS INCLUDED IN YOUR APPLICATION. YOU MAY DELETE THE BLUE TEXT BEFORE SUBMISSION

4. Participant Population.

One hundred individuals receiving buprenorphine/naloxone as opioid replacement therapy (ORT) will be screened randomized. We included individual receiving ORT because we specifically target risk of relapse in a treatment-seeking population. No vulnerable population will be included in the study.

INCLUSION CRITERIA

- ~Male or female (50%), 18 to 70 (inclusive) years of age;
- Currently meets DSM-5 criteria for OUD;
- Currently on a stable dose of buprenorphine/naloxone or methadone for at least 3 months:
- In good health as confirmed by medical history, physical examination and blood work (AST/ALT; bilirubin, creatinine clearance within normal limit);
- Willing to take medication and adhere to the study procedures;

- Understand informed consent and questionnaires in English at an 8th grade level;
- Clinical Opiate Withdrawal Scale (COWS) = 0 at study screening and prior laboratory sessions.

> EXCLUSION CRITERIA

- Women who are breastfeeding, test positive for pregnancy or are unwilling to use medically-approved birth control;
- Liver function within 5x the Upper normal limits (AST/ALT) and renal function within 2x the Lower Normal Limit (bilirubin, creatine clearance).
- Suicide attempts in the last three months;

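### The protocol's sample size paragraph contradicts itself (67 needed, 50 completers planned; 50 + 13 is not 80; 0.63 treated as adequate power) and powers a two-group design, not the crossover in use

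*Protocol*

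**What the plan says.** The sample size paragraph is in Protocol Part III, section 4 (Participant Population). It takes alpha 0.05 and f = 0.35, with the effect size drawn from a between-subjects study, and states: "two group independent variable and three covariates in ANCOVA, the *N* is 67 to detect 0.80 power". It then allows for loss: "With an additional 0.20 to account for attrition [N = 50 (completers) + 13 = 80 (enrolled". For Aim 2: "The estimated power at N = 67, with the addition of an interaction term (for Aim 2) would be = 0.63". It concludes that "the calculated sample size is well powered to address the hypothesis of the main medication effect (Aim 1) and of the interaction effect"; the interaction meant here is the one in Aim 2.

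The numbers of participants are given in three places:

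- Section 2 (Specific Aims): "individuals with OUD (*N*=50) who are currently receiving treatment with buprenorphine/naloxone or methadone will be randomized".
- Section 4, opening sentence: "One hundred individuals receiving buprenorphine/naloxone as opioid replacement therapy (ORT) will be screened randomized".
- Section 4, before the sample size paragraph: 100 screened, and "80 will be randomized, with 50 expected to complete the study".

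On design, section 3 says "This study will use a within subject design with oxytocin vs. oxytocin-matching placebo", crossed with yohimbine against its placebo. The SAP (Study design, setting and approval) says that the study began as a between-subjects trial and became a crossover after the pandemic. The SAP's Statistical analysis section gives no power figure. It calls the trial preliminary and the sample modest, and says that the within-subject design helps power.

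**The concern.** A sample size paragraph should lead from an effect size, through a required number, to the number enrolled. Here the chain breaks at each step. The required number (67) is not the planned number of completers (50). The attrition sum does not add up. The favourable conclusion covers an Aim 2 test for which the paragraph itself reports 0.63. And the calculation compares two independent groups, whereas each participant is now meant to receive both oxytocin and placebo.

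As written, a reader cannot tell how many were to be randomized, what loss was assumed, or what power the crossover was planned to have. That matters most when a null craving result, or a null stress interaction, has to be interpreted.

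**Working it through.** **Inputs from the sample size paragraph.** f = 0.35, alpha 0.05, two groups, three covariates, N = 67 for 0.80, attrition 0.20, Aim 2 power 0.63 at N = 67. Planned completers: 50. Equal allocation is assumed.

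**1. The plan's own figure.** ANCOVA F test with noncentrality λ = f²N, df1 = 1, df2 = N − 2 − 3.

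| N | λ = 0.1225 × N | df2 | Power |
|---|---|---|---|
| 66 | 8.085 | 61 | 0.799 |
| 67 | 8.208 | 62 | 0.805 |
| 64 | 7.840 | 59 | 0.786 |
| 50 | 6.125 | 45 | 0.678 |

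So 67 is the smallest N that reaches 0.80, and the stated figure is right. At 50 completers the same test has power 0.68.

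**2. The bracket.** 50 + 13 = 63, not 80. Two different chains fit the number 13:

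- 67 × 0.20 = 13.4, and 67 + 13 = 80.
- 50 / 0.8 = 62.5, rounded up to 63 = 50 + 13.

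The bracket starts with the second chain and ends with the first.

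**3. The attrition rate.** From 80 randomized to 50 completing is 1 − 50/80 = 37.5%, not 20%. If 50 in the bracket is read as a slip for 67, then 80 × 0.8 = 64 completers, with power 0.786. Keeping 67 after a 20% loss would need 67/0.8 = 83.75, that is 84.

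**4. The Aim 2 figure.** The paragraph gives neither the effect size nor the degrees of freedom behind 0.63. Two readings reproduce it at N = 67:

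- f = 0.35 with 3 numerator df: 0.634 to 0.636 for df2 from 59 to 62.
- 1 df with λ = 5.42, which means f = √(5.42/67) = 0.284.

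With f = 0.35 and 1 df, power would be 0.80, not 0.63. At N = 50 the two readings give 0.49 and 0.50.

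**5. What a within-person calculation might give (illustration only).** Assumptions: 50 complete pairs; d = 0.70, the two-group equivalent of f = 0.35 (d = 2f); within-person correlation ρ from 0 to 0.7. The documents give no correlation. Because f is an ANCOVA effect, d is in covariate-adjusted SD units, so ρ must be the correlation left after that adjustment.

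Aim 1: paired t test, dz = 0.70/√(2(1 − ρ)), noncentrality dz√50, df = 49.

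Aim 2: the λ behind 0.63 (5.42 with 1 df, or 8.21 with 3 df) is multiplied by [50/(2(1 − ρ))]/(67/4). This is the ratio of information on a drug contrast in 50 pairs to that in 67 people split between two groups. Here df2 = 47 or 45.

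| ρ | Aim 1 | Multiplier | Aim 2, 1 df | Aim 2, 3 df |
|---|---|---|---|---|
| 0 | 0.929 | 1.49 | 0.796 | 0.813 |
| 0.3 | 0.984 | 2.13 | 0.915 | 0.935 |
| 0.5 | 0.998 | 2.99 | 0.976 | 0.987 |
| 0.7 | >0.999 | 4.98 | 0.999 | >0.999 |

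**6. At the number achieved.** The SAP's Missing data reporting section lists 16 within-subject and 4 between-subject participants. The Aim 1 formula with 16 pairs (df = 15) gives 0.46, 0.60, 0.74 and 0.92 over the same correlations. These are after-the-fact figures, not planning figures.

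**7. The Aim 2 test.** The SAP's Outcomes paragraph specifies the oxytocin and yohimbine main effects and their interaction. Trait anxiety and stress enter as covariates. No oxytocin-by-baseline-stress term is listed, so no specified test corresponds to the Aim 2 power figure.

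**The case against.** For Aim 1, the favourable conclusion is attached to the calculated sample size. That is 67, where power is 0.80 as intended. This stands: a reader might infer that the Aim 1 statement is false on its own figures, and it is not. The fault is in carrying it over to 50 completers and to a different design.

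A reader might also count 100 as a third number randomized. The documents do not support that. The opening sentence of section 4 is garbled, and the same section later says clearly that 100 are to be screened. The conflict that remains is 50 randomized (section 2) against 80 (section 4). The 50 may be loose wording for completers.

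The bracket could be a single slip, 50 typed for 67. That would repair the sum, but 50 also stands outside the bracket as the expected number of completers, so the gap between 67 and 50 and the 37.5% loss remain.

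The SAP does not repeat the claim of good power. It presents the trial as preliminary and describes a locked database, so correction now affects the record and not the conduct. This lessens the practical weight but supplies no figure to replace the protocol's.

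Finally, the upper crossover values in the illustration may flatter the design. Covariate adjustment removes some between-person variance, so raw correlations of 0.5 to 0.7 would count that gain twice.

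**Conclusion.** The justification is inconsistent within itself and does not describe the design in use. On its own two-group basis, power at the planned 50 completers is 0.68 for Aim 1 and about 0.49 to 0.50 for Aim 2, not 0.80 and 0.63. The implied loss is 37.5% against 20%. The Aim 2 conclusion contradicts the 0.63 reported in the sentence before it.

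The tempting stronger reading is that the trial was planned with too few participants. The documents do not show that. A two-group power figure is not the power of a crossover, and under the stated assumptions 50 completers could give ample power for Aim 1 and possibly for Aim 2. For the same reason, raising the target to 67 is not the remedy.

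That the calculation was carried over from the earlier between-subjects design is probable, given its two-group form, its between-subjects source and the SAP's account of the change. No document says so.

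The reproduction of 67 and the arithmetic on the bracket and the loss use only the protocol's figures and equal allocation. The Aim 2 value at 50 depends on which unstated basis lies behind 0.63, though both readings agree closely. The crossover figures rest on the assumed d and correlations.

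**What to change.** In Protocol Part III, section 4, correct the bracket and make the attrition rate agree with the numbers randomized and completing. State one number randomized in sections 2 and 4, and reword the garbled opening sentence of section 4.

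Withdraw the claim of good power for Aim 2 as a conclusion from 0.63. For Aim 1, stop applying 0.80 at N = 67 to 50 completers.

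Replace the two-group ANCOVA with a within-person calculation at 50 completers, one for Aim 1 and one for the Aim 2 drug-by-baseline-stress interaction. For each, state the effect size, the degrees of freedom and a range of within-person correlations, and say that these are the correlations left after covariate adjustment. In the SAP, either point to the model term that tests Aim 2 or say that none was specified. Mark these corrections, and any power quoted at the achieved number, as made after the fact.

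The cost is one recalculation and some wording in both documents, with no added patients or visits. The claim of good power has to be withdrawn as written; the new calculation may restore it for Aim 1 and possibly for Aim 2.

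### The 0.63 power stated for Aim 2 matches a 3-df test, not the 1-df oxytocin-by-stress interaction at the printed effect size (0.80), and it is a between-subjects figure at N = 67 for a trial now planned as a crossover with 50 completers

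*Protocol*

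**What the plan says.** The sample size paragraph (Protocol Part III, section 4, Participant Population) assumes a "standard threshold, α = 0.05", sizes the trial "for med-large effect (f = 0.35"), and describes the model as "two group independent variable and three covariates in ANCOVA". It reports that N "is 67 to detect 0.80 power". For Aim 2 it adds one sentence: "The estimated power at N = 67, with the addition of an interaction term (for Aim 2) would be = 0.63". It gives no numerator degrees of freedom, number of cells or effect size for that interaction.

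It then concludes: "Therefore, the calculated sample size is well powered to address the hypothesis of the main medication effect (Aim 1"), and the same sentence extends the claim to the Aim 2 interaction with stress and anxiety. The paragraph expects 50 completers.

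Aim 2 (Protocol Part III, section 2, Specific Aims) concerns the sessions with yohimbine-matched placebo. Its hypothesis is that "opioid craving will be reduced in the oxytocin condition only among individuals with higher levels of stress at baseline". No cut-point for higher stress is given.

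Section 3 (Materials, Methods and Analysis) describes a within-subject design. The SAP confirms that the trial began as a between-subjects study and was changed to a crossover. It states that "All statistical tests were two-tailed". In its Outcomes paragraph the SAP specifies an oxytocin-by-yohimbine interaction and enters stress (PSS) only as a covariate. It lists no oxytocin-by-stress term and gives no new power figure for Aim 2.

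**The concern.** Whether the oxytocin effect depends on one baseline stress measure is a single-degree-of-freedom question, whether stress is split or entered linearly. In a fixed-f calculation, adding one such term costs one error degree of freedom and leaves power almost unchanged. A fall from 0.80 to 0.63 at the same N therefore means that something else changed in the calculation, and the protocol does not say what.

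The figure supports the claim that Aim 2 can be answered. If it belongs to a different test, a different effect size or the superseded design, readers have no sound basis for weighing a non-significant interaction. Such a result could be taken to show that stress does not matter, when the trial may simply have been unable to tell.

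**Working it through.** **Inputs from the documents.** f = 0.35, alpha = 0.05, two groups, three covariates, N = 67 and 50 completers (protocol, sample size paragraph). Two-sided testing and 16 within-subject participants (SAP). For two equal groups d = 2f = 0.70.

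**Formula.** Noncentral F with noncentrality lambda = f² × N and error df = N − groups − covariates.

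**Step 1: reproduce the main-effect figure.** With 1 numerator df:
- N = 66: lambda = 0.1225 × 66 = 8.085, error df = 61, power 0.799.
- N = 67: lambda = 0.1225 × 67 = 8.2075, error df = 62, power 0.805.

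So 67 is the smallest N that reaches 0.80. The plan's figure reproduces, and this is very probably the method that was used.

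**Step 2: look for 0.63.** Keep f = 0.35 and N = 67, with four cells and three covariates (error df = 67 − 4 − 3 = 60):

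| Numerator df | Power |
|---|---|
| 1 | 0.805 |
| 2 | 0.706 |
| 3 | 0.635 |
| 4 | 0.579 |

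Only 3 df comes close to the printed value. Varying the groups from 2 to 8 and the covariates from 0 to 4 moves the 3-df result only between 0.632 and 0.637, so the match says nothing about the number of cells. A 1-df test gives 0.63 only if f is about 0.285, a value that is not printed.

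**Step 3: the 1-df interaction at the printed f.** Power is 0.80 at N = 67. At N = 50, lambda = 0.1225 × 50 = 6.125, error df = 43 and power is 0.68.

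**Step 4: the pattern stated in Aim 2, under assumptions.** Assume d = 0.70 in higher-stress participants, zero in the others, and a share p of higher-stress participants. For equal allocation the interaction effect size is f = 0.70 × √(p(1 − p)) / 2. At p = 0.5 this is 0.70 / 4 = 0.175.
- N = 67: lambda = 0.030625 × 67 = 2.05, power 0.29.
- N = 50: lambda = 0.030625 × 50 = 1.53, power 0.23.
- N = 67 with p = 0.25, 0.33 or 0.40: power 0.23, 0.26 or 0.28. The equal split is the most favourable.

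If f = 0.35 is instead the average oxytocin effect over everyone, with an equal split, d in the high-stress half is 1.40, the interaction f is 1.40 / 4 = 0.35, and power at N = 67 is again 0.80. The between-subjects answer thus runs from about 0.23 to 0.80 at N = 67, depending on what f = 0.35 is taken to mean.

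**Step 5: the crossover now planned.** Compare the paired oxytocin-minus-placebo difference between equal high- and low-stress halves, with d = 0.70 in the high half and zero in the low half. With within-person correlation rho (assumed; not in the documents), the SD of the difference is √(2(1 − rho)), its standard error between halves is √(2(1 − rho)) × √(4/N), and the t test has N − 2 df.

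| rho | N = 50 | N = 16 |
|---|---|---|
| 0.3 | 0.54 | 0.20 |
| 0.5 | 0.68 | 0.26 |
| 0.7 | 0.88 | 0.39 |

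Worked case: for rho = 0.5 and N = 50 the standard error is 1.0 × √(4/50) = 0.283, the noncentrality is 0.70 / 0.283 = 2.475, and power is 0.68.

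**The case against.** The strongest reply is that nothing has been shown to be miscalculated. The protocol states neither the df nor the interaction effect size. A reader might infer that 0.63 is the power of a four-group omnibus test that mixes the oxytocin main effect, the stress main effect and their interaction. The documents do not establish that. A joint test of oxytocin by three covariates (3 df, error df 59) gives 0.634 and contains no main effects, and a 1-df test with f near 0.285 fits as well. This part of the reply stands: one can say that 0.63 matches a 3-df test, not which test it was.

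A reader might also infer that Aim 2 really has power of only about 0.29, so that a null result is to be expected even if the hypothesis is true. That goes too far. The 0.29 needs three assumptions that the documents do not supply: d = 0.70 inside the high-stress group, no effect outside it, and an equal split. It also belongs to the superseded between-subjects design. In the crossover at 50 completers the same pattern gives 0.54 to 0.88, a range that contains 0.63. Low power reappears at the 16 within-subject participants, but that reflects the number obtained and is not an error in the printed figure.

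Finally, the SAP presents the trial as preliminary, with sample size balanced against feasibility. That is reasonable, but it does not withdraw or replace the protocol's power statement.

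**Conclusion.** The point holds in a limited form. On the plan's own inputs, the power stated for Aim 2 is not that of the 1-df test that Aim 2 calls for: 0.63 is printed, against 0.80 at N = 67 and 0.68 at 50 completers. It rests on an unstated df or effect size. It also describes a two-group between-subjects analysis at an N above the expected number of completers, while the protocol plans a crossover.

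That the numerical overlap with the crossover range includes 0.63 does not rescue the figure, because the range depends on a correlation and a stress pattern that the plan never states. The direction of the error is open: depending on these assumptions, the true power for Aim 2 may be above or below 0.63. What the documents do not support is the step from this figure to the claim that the sample is well powered for Aim 2.

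**What to change.** - Replace 0.63 with the power of the 1-df oxytocin-by-baseline-stress contrast, computed on the paired oxytocin-placebo difference in the yohimbine-placebo sessions at the expected number of completers. State the df, the assumed interaction effect size, the stress split (or linear form) and a range of within-person correlations.
- Remove Aim 2 from the well-powered sentence unless the recomputed figure supports it.
- Report the interaction estimate with its 95% confidence interval, and say in advance that a non-significant interaction is inconclusive.

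The cost is one recalculation and a few sentences. Enrolment and procedures do not change. The downside is a less certain, and possibly less favourable, stated power for Aim 2.
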